7.2 Inclusion Criteria

- 1. Age >18 years
- Previous clinical diagnosis of heart failure with current NYHA Class II-IV symptoms LVEF≤0.40 within 2 years prior to consent, and ≥3 months after a major change in cardiac status (i.e. CABG or CRT).
- 3. Serum ferritin between 15-100 ng/ml or serum ferritin between 100-299 ng/ml with transferrin saturation <20%
- 4. Hemoglobin 9.0-15.0 g/dL (males), 9.0-13.5 (females) at time of enrollment
- 5. Evidence-based medical therapy for HF (including beta-blocker and ACE-inhibitor/ARB unless previously deemed intolerant and diuretics as necessary) with ≤100% change in dose for 30 days prior to randomization
 - a. Changes in diuretic dose guided by a patient-directed flexible dosing program are considered stable medical therapy
- 6. Willingness to provide informed consent

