9.3 Screening Phase (≤ 1 month)

Suitable candidates will be approached by investigators regarding the study and be provided with detailed study information and a copy of the informed consent form. Informed consent will be obtained from eligible candidate to undergo further evaluations and potential enrollment as required by the local institutional review boards. There can be no changes in the protocol without the prior agreement of the Heart Failure Network (HFN) Steering Committee.

Screening procedures include the following:

- Written informed consent for the study protocol. (Section 17.3)
- Complete medical history:
 - o HF etiology, duration, and severity

- NYHA class assessment
- History of bleeding, Fe exposure or erythropoietin stimulating agents
- Medication review
- Other exposures within the time-frames specified in Figure 10.1
- Physical examination
- Documentation of LVEF ≤0.40:
 - Clinically available echocardiography within 24 months of informed consent may be used to qualify the patient for study inclusion.
 - However, if the patient had an intercurrent cardiac procedure that may alter the LVEF significantly (e.g. CRT) since the last echocardiography, the LVEF assessment used for inclusion must be obtained at least 3 months since the procedure.
- Phlebotomy for: (processed at local laboratory)
 - Fe studies* (Fe, ferritin, transferrin/TIBC, transferrin saturation)
 - Complete blood count*
 - Complete chemistry panel* (sodium, potassium, chloride, carbon dioxide, BUN, creatinine, glucose, ALT, AST, alkaline phosphatase and total bilirubin)

*Clinically available or pre-screening laboratory studies

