15.2 Analysis of the Primary Endpoint

A general linear model with the change in peak VO_2 measured at 16 weeks as the response variable and predictor variables including a treatment indicator and the baseline measure of peak VO_2 will be used in the primary analysis. The treatment effect will be determined by the point estimate and 95% confidence interval for the treatment indicator variable.

A secondary analysis of the peak VO₂ outcome will be conducted using a repeated measures analysis. For this analysis all measurement of peak VO₂(including baseline) will be treated as response variables. The following covariates will be included in the regression model treatment group, time period, treatment group * time period interaction, baseline VO₂ and baseline Fe level. An unstructured correlation matrix will be assumed for the repeated measures within subjects. The mixed model repeated measures analysis will be estimated using SAS PROC MIXED.

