17.3.2 Cardiopulmonary Exercise Testing Core Laboratory

Massachusetts General Hospital will serve as the core laboratory for cardiopulmonary exercise testing. Comprehensive site certifications will be performed for participating centers and CPETs will be electronically transferred to the MGH Core Laboratory. Detailed CPET procedures are outlined in the manual of operations.

Measurement Methods: The following procedures or measurements will be performed at various time points throughout the study (see Human Subjects for details). CPETs will be performed on each subject at baseline and 16 weeks. The lag in VO₂ increment following initiation of constant workload exercise, before steady state is reached, is the oxygen deficit (Fig 16.3.3).⁴⁵ Phase I of this period is a brief cardiodynamic phase that reflects increase in cardiopulmonary blood flow. The shallower phase II reflects O₂ extraction that we hypothesize is strongly influenced by Fe. The O₂ deficit will be measured as the time constant from the monoexponential equation: VO₂(t) = VO₂(baseline) + A(1-e^{-t/}r), where t is the time after the start of exercise, A is the amplitude of VO₂ response, and τ is the time constant.⁴⁶ Recovery O₂ kinetics (O₂ debt, denoted in **Fig 16.3.3**) correlate with recovery of energy stores as well as

blood and tissue O_2 stores after exercise.⁴⁷ Both O_2 deficit and debt are increased in HF and are related to symptoms during sub-maximum exercise.

Fig 16.3.3 O₂ kinetics during low level CPET

The CPET will also measure the primary endpoint, peak VO₂ and will consist of a 10 watt/min incremental load performed according to the HF Network CPET Core Lab Manual of Operations to derive the primary endpoint ΔpVO_2 , as well as VO₂ at AT and OUES.

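### In the secondary repeated-measures model of section 15.2, baseline iron has no interaction with time, so it cannot adjust the treatment effect on change in peak VO2

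*Protocol*

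**What the plan says.** Protocol section 15.2 gives two analyses of peak VO2. The primary one is a general linear model for change at week 16, with treatment and baseline peak VO2 as predictors. It contains no iron term.

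The secondary one is a repeated-measures model in which "all measurement of peak VO₂(including baseline) will be treated as response variables". Its covariates are treatment, time period, "treatment group * time period interaction, baseline VO₂ and baseline Fe level". On the covariance it says: "An unstructured correlation matrix will be assumed for the repeated measures within subjects".

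No iron-by-time and no baseline-VO2-by-time term is listed. Section 17.3.2 fixes the number of visits that supply the outcome: "CPETs will be performed on each subject at baseline and 16 weeks". The schedule in Appendix A agrees.

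**The concern.** A covariate with the same coefficient at every visit shifts the whole profile of a participant up or down. It says nothing about the change between visits. When baseline is one of only two responses, the effect of interest is the difference in change, and that is how sections 5 and 12.3 frame the endpoint. A time-constant iron term drops out of that difference.

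This is the only peak VO2 analysis in section 15.2 that names iron. A reader who sees iron among the covariates would take its treatment effect on change to be adjusted for baseline iron, and it would not be. At stake is some precision if iron predicts change and, under particular dropout patterns, protection against bias from missing week-16 tests.

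**Working it through.** **The plan's own figures.** The protocol gives no figure for the repeated-measures model. Its sample size reproduces. For a difference of 1.0 and SD 2.0 ml/kg/min, two-sided 0.05, the noncentral t gives power 0.8999 with 85 per group and 0.903 with 86. Then 86 / (1 − 0.20) = 107.5, so 108 per group, or about 220 in total. None of this is in dispute.

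**Algebra.** Let A be treatment (0/1), B baseline VO2, F baseline iron, and Y0 and Y16 the two responses. As listed:

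- E[Y0] = α + τA + βB + γF
- E[Y16] = α + δ + (τ + θ)A + βB + γF
- E[Y16 − Y0] = δ + θA

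Both γF and βB are gone, and θ is the treatment-by-time term. With complete data the likelihood splits into a part for the change D = Y16 − Y0, which holds only δ, θ and var(D), and a part for Y0 given D, whose intercept and treatment coefficient are free. So the estimate of θ is the raw difference in mean change, with or without iron, whatever the within-subject covariance.

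**Model exactly as listed.** Baseline VO2 predicts the baseline response perfectly, so the likelihood has no maximum. One simulated trial was used (n = 220, 20% of week-16 values missing, residual correlation set to 0 and week-16 residual variance set to 2). The baseline residual SD was driven towards 0:

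| Baseline residual SD | Log-likelihood | Slope on baseline VO2 | Iron coefficient | Treatment-by-time with iron | Treatment-by-time without iron |
|---|---|---|---|---|---|
| 1 | −180.1 | 0.924 | 0.104 | 1.4388 | 1.4332 |
| 0.1 | 322.9 | 0.999 | 0.0014 | 1.4421 | 1.4420 |
| 0.01 | 829.4 | 1.000 | 0.00001 | 1.4421 | 1.4421 |
| 0.001 | 1336.0 | 1.000 | 0 | 1.4421 | 1.4421 |

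The raw difference in change among completers is 1.4421. In this limit the iron term vanishes and the slope on baseline VO2 is forced to 1.

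**Baseline VO2 dropped as a covariate, arm-specific baseline means.** The two-visit unstructured model was fitted by REML, 40 simulated trials per setting. Assumed, because the protocol gives no values: baseline to week-16 correlation 0.7, iron to baseline VO2 correlation 0.3 to 0.5, iron effect on week 16 given baseline 0 to 0.8 ml/kg/min per SD.

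- Complete data (n = 172): adding the iron main effect moves treatment-by-time by less than 2e-13. The SE is 0.2331 with and without it in the weak-iron setting, and is likewise unchanged in the others.
- 20% missing (n = 220): the main effect moves it by rms 0.012 to 0.033, against an SE of about 0.23.
- Iron-by-time added, complete data: the estimate moves by rms 0.02 to 0.07. The SE goes from 0.233 to 0.232 (weak iron effect) or from 0.242 to 0.232 (strong).
- Iron-by-time added, 20% missing: the estimate moves by rms 0.03 to 0.09. The SE goes from 0.231 to 0.229 or from 0.238 to 0.224.

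**Size over repeated trials.** 1,500 simulated trials of 220, with assumed baseline SD 3 and residual SD of change 1.8 ml/kg/min.

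- Precision: the SD of the estimate is 0.262 without iron and 0.262 with the main effect. With iron-by-time it is 0.257 if iron explains 4% of the variance of change and 0.247 if it explains 9%. The gains are 1 − 0.257/0.262 = 1.9% and 1 − 0.247/0.262 = 5.7%. At 1% the gain is negligible.
- Bias, if 20% are missing and dropout depends on iron in one arm only (assumed log-odds −0.8 per SD): 0.06 to 0.09 without iron, 0.06 to 0.08 with the main effect, about 0.00 with iron-by-time. At 1% of variance the bias is about 0.03.

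**The case against.** **The inertness is a by-product of a larger defect, baseline VO2 on both sides.** Largely true. If baseline is taken out of the responses, the model becomes a week-16 ANCOVA and the iron main effect adjusts fully, with no interaction needed. If baseline stays as a response only and the arms share one baseline mean, the main effect works in part. With assumed iron to baseline VO2 correlation 0.3, baseline slope 0.7 and iron explaining 9%, the SD fell from 0.255 to 0.246 with the main effect and to 0.244 with iron-by-time. With correlation 0 the recovery was only partial. Under the one-arm dropout above, bias in that common-mean model stayed at 0.058 to 0.081 with the main effect and came within 0.004 of zero with iron-by-time. So a reader should not infer that iron stays inert after every repair. It does after one natural repair, dropping baseline VO2 as a covariate with arm-specific baseline means.

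**Section 15.2 does not name the contrast to be reported.** Correct. Once baseline VO2 is off the covariate list, a plain week-16 arm difference (treatment plus treatment-by-time) does move with iron, by rms 0.05 to 0.16. The point concerns the effect on change.

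**Iron level might mean serum iron.** A reader might infer this, because section 9.3 lists "Fe, ferritin, transferrin/TIBC, transferrin saturation" as separate tests while section 7.2 defines deficiency by ferritin ("Serum ferritin between 15-100 ng/ml", or a higher band combined with low transferrin saturation). The protocol does not support that reading as an error. Sections 5.1 and 9.2 speak of measuring Fe levels in order to find patients with iron deficiency, which is shorthand for iron studies. The choice of marker belongs in the SAP.

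**The magnitude rests on assumptions.** It does. Nothing in the protocol indicates that dropout depends on iron in one arm only, or how much of the change iron explains.

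**Conclusion.** The point holds for the secondary analysis and for the treatment effect on change. With complete data the cancellation is exact algebra, for the model as listed and for the version without baseline VO2 as a covariate and with arm-specific baseline means. With missing week-16 values, the model as listed was checked in its degenerate limit with zero residual correlation, where iron again does nothing. Under other covariances small shifts are possible, but a model whose likelihood has no maximum gives no dependable adjustment.

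The consequence is modest. Allocation is randomised and the primary model needs no iron term to be valid. The precision forgone is about 2% to 6% under the assumed 4% to 9% of variance. The largest bias found, 0.09 ml/kg/min, is 9% of the 1.0 ml/kg/min minimally important difference in section 15.5, and it needs the assumed one-arm dropout. A reader might infer that the trial's main result is biased or unadjusted in a harmful way. The protocol does not support that.

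**What to change.** Amend the second paragraph of section 15.2, or settle it in the SAP before unblinding, in one of two ways:

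1. Take baseline peak VO2 out of the response vector and keep baseline VO2 and baseline iron as covariates. With two visits this is a week-16 ANCOVA, in effect the primary model plus iron.
2. Keep baseline peak VO2 as a response, remove it from the covariates, and add a baseline iron-by-time interaction. Name treatment-by-time as the reported contrast.

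Rewording the iron term alone would leave baseline VO2 as both response and covariate, and the likelihood would still have no maximum.

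The cost is a change of wording. Iron studies are already collected at baseline (section 10.1). Option 2 adds one parameter per iron marker. Option 1 uses only participants with a week-16 test.

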15.3 Analysis of Secondary and Exploratory Endpoints

Summaries of continuous variables will be displayed using the mean, standard deviation, median, and 25th-75th percentiles. For nominal variables, the number and percentages in each category will be presented. General linear models and nonparametric approaches will be used to analyze the continuous outcomes. For binary outcomes, Chi-square tests and Fisher's exact test will be used for unadjusted comparisons. For adjusted comparisons, logistic regression analysis will be used to compare oral Fe vs. placebo with the estimated odds ratio and associated 95% confidence interval.

For the composite exploratory endpoint of time to death and heart failure hospitalization, unadjusted time-to-event comparisons will be conducted using Kaplan-Meier survival estimates and log-rank tests. For adjusted analyses, Cox proportional hazards regression models will be used to estimate hazard ratios. Heart failure hospitalization is defined as an event that occurred primarily because of the documented presence of at least:

Clinical manifestations of worsening heart failure

• Use of additional or increased pharmacologic or mechanical interventions directed at the treatment of heart failure

15.4 Analysis of Safety Data and Statistical Monitoring Plan

Interim data analysis for efficacy and futility will not be conducted due to relatively small size and short duration of this clinical trial. Safety data, summarized at the treatment level, will be assessed approximately every 6 months by the NHLBI-appointed DSMB. The safety analyses will be based on the entire ITT population. Safety will be evaluated by comparing the occurrence of AEs and changes in laboratory values of the active arm compared to placebo. The number and percentage of participants experiencing AEs will be tabulated by treatment group, body system, and preferred term. The percentages between treatment groups will be compared using Fisher's exact test.

15.5 Sample Size Justification

The proposed sample size of 220 subjects will be adequate to address the primary objectives of the study. As in the HFN's PhosphodiesteRasE-5 Inhibition to Improve CLinical Status And

EXercise Capacity in Diastolic Heart Failure (RELAX) clinical trial, the assumed minimally important difference for peak VO₂ is 1.0 ml/kg/min. Based on prior studies within the HFN, a conservative estimate of 2.0 ml/kg/min for the standard deviation for peak VO₂ (ml/kg/min) will be assumed. Using a two-sample t-test a sample size of 172 subjects (86 per group) will provide 90% power to detect the minimally important difference. These calculations assume a common standard deviation of 2.0 ml/kg/min and a two-sided type I error of 0.05. Allowing for 20% missing data would result in a sample size of roughly 108 per group or a total sample size of approximately 220 subjects.

For secondary endpoints, a sample size of greater than 86 subjects per group will provide greater than 90% power to detect differences greater than 0.5 standard deviations for continuous endpoints. These calculations are based on the two-side t-test and assume that the data are normally distributed with a common standard deviation. Similar sample sizes will provide greater than 80% power to detect differences larger than 0.43 standard deviations.

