5.2 Baseline Evaluation Phase and Randomization

After providing written informed consent, research participants will complete all baseline procedures, including: clinical evaluation, blood samples, and CPET. Participants who fulfill all the inclusion criteria and none of the exclusion criteria will be randomized. Eligible participants will be randomized with a 1:1 allocation ratio to either oral Fe polysaccharide 150mg twice daily or matching placebo.

During randomization visit, participants will be counseled on optimal study drug administration (after 2 hours of fasting when possible while avoiding concomitant ingestion of proton pump inhibitors, H_2 blockers, dairy products or calcium supplements). Arrangements will be made for an initial phone call follow-up 7 days after randomization. Participants will receive a written description of the study with contact numbers of study staff to present to their usual care provider(s).

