12 OUTCOME DETERMINATIONS

12.1 Primary Endpoint

1. Peak VO₂ (ml/min) as measured by CPET.

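### The 90% power is calculated in ml/kg/min, but the primary endpoint is defined in ml/min and the protocol gives no conversion

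*Protocol*

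**What the plan says.** Section 12.1 names the primary endpoint as "Peak VO₂ (ml/min) as measured by CPET", and the Executive Summary (Section 2) gives the same unit. Section 15.2 fixes the primary analysis as a general linear model for 16-week change, adjusted for the baseline value: "measured at 16 weeks as the response variable and predictor variables including a treatment indicator and the baseline measure of peak" (the quote stops just before the symbol for oxygen uptake). Sections 4.1, 5 and 15.2 name no unit.

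Section 15.5 uses another unit throughout: "the assumed minimally important difference for peak VO₂ is 1.0 ml/kg/min", and "a conservative estimate of 2.0 ml/kg/min for the standard deviation for peak VO₂ (ml/kg/min) will be assumed". It continues: "Using a two-sample t-test a sample size of 172 subjects (86 per group) will provide 90% power", assuming "a common standard deviation of 2.0 ml/kg/min and a two-sided type I error of 0.05". The last step is: "Allowing for 20% missing data would result in a sample size of roughly 108 per group", rounded to about 220 in total. The section does not say whether 2.0 is the SD of the value at one visit, of the 16-week change, or of the residual after adjustment for baseline. It gives no correlation between baseline and week 16.

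**The concern.** The power statement and the endpoint definition are on different scales. Dividing by body weight is not a fixed change of unit such as litres to millilitres, because each patient has a different divisor. The ratio of difference to SD, which determines power, therefore need not be the same on the two scales. Patients of different weight who have the same peak VO₂ per kg differ in ml/min, and that spread enters the SD.

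The reader is told that 86 completers per group give 90% power, but for a quantity that the protocol does not name as its primary endpoint. A null result reported in ml/min could not be set against the 1.0 ml/kg/min difference that the trial was designed to detect. The protocol also leaves open which of the two scales the primary p-value belongs to.

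**Working it through.** **1. The protocol's own figure.** Inputs from Section 15.5: difference 1.0, SD 2.0, two-sided α 0.05, two-sample t-test, 86 per group. Allocation is 1:1 (Section 5.2).
- Noncentrality = 1.0 / (2.0 × √(2/86)) = 3.28 on 170 degrees of freedom, which gives power of 90.3%.
- The smallest n per group for 90% power is 86 by the exact t calculation.
- 86 / 0.8 = 107.5, so 108 per group, 216 in total, rounded to about 220.

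The printed arithmetic reproduces.

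**2. Does baseline adjustment undermine it in ml/kg/min?** Let r be the correlation of peak VO₂ per kg between baseline and week 16 (not in the protocol; a range is assumed), with equal variance at both visits. One degree of freedom is removed for the covariate.

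| r | Residual SD if 2.0 is the raw SD: 2.0√(1−r²) | Power | Residual SD if 2.0 is the SD of change: 2.0√((1+r)/2) | Power |
|---|---|---|---|---|
| 0 | 2.00 | 90.3% | 1.41 | 99.6% |
| 0.3 | 1.91 | 92.8% | 1.61 | 98.1% |
| 0.5 | 1.73 | 96.4% | 1.73 | 96.4% |
| 0.7 | 1.43 | 99.5% | 1.84 | 94.3% |

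Neither residual SD can exceed 2.0, so 90.3% is a floor under both readings.

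**3. The same design in ml/min.** The protocol gives no inputs for this, so all of the following are assumptions:
- mean peak VO₂ of 14 ml/kg/min, and 2.0 as the SD of the raw value;
- body weight with mean m and coefficient of variation (CV) 20%, unchanged over 16 weeks and independent of peak VO₂ per kg;
- a target difference of 1.0 × m ml/min, ignoring any extra variance if heavier patients gain more in ml/min.

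Dividing through by m (or m² for variances), with k = 1 + 0.20² = 1.04:
- Variance at each visit = (14² + 2²) × 1.04 − 14² = 208 − 196 = 12, so the SD is 3.46 instead of 2.0.
- Covariance between visits = (14² + 4r) × 1.04 − 14² = 7.84 + 4.16r.
- Residual variance = 12 − (7.84 + 4.16r)² / 12.

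| r (per kg) | Correlation in ml/min | Residual SD ÷ m | Power at 86 per group |
|---|---|---|---|
| 0.3 | 9.088/12 = 0.757 | 2.26 | 82% |
| 0.5 | 9.92/12 = 0.827 | 1.95 | 92% |
| 0.7 | 10.752/12 = 0.896 | 1.54 | 99% |

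The residual SD equals 2.0 when the ml/min correlation is √(1 − 4/12) = 0.816, that is r = (12 × 0.816 − 7.84)/4.16 ≈ 0.47. Below that value, power drops under the stated figure.

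**4. Sensitivity.** Replacing 1.04 by 1 + CV², CVs of 10%, 15%, 20% and 25% give 88%, 85%, 82% and 80% power at r = 0.3, and 94%, 93%, 92% and 90% at r = 0.5.

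If 2.0 is instead the SD of change, the raw per-kg variance is 4/(2(1−r)). At r = 0.3 this is 2.857. The variance in ml/min is then 198.857 × 1.04 − 196 = 10.81, the covariance is 196.857 × 1.04 − 196 = 8.73, and the residual SD is √(10.81 − 8.73²/10.81) = 1.94, giving 92% power. At r = 0.7 and 0.9 the same steps give 91% and 90%. The meaning of 2.0 therefore matters more in ml/min than in ml/kg/min.

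**The case against.** The strongest defence is that sizing by t-test and analysing with baseline adjustment is common and safe, since a reliable correlation is often not available in advance. That stands. A reader might infer that 90% and 86 per group fail for the primary analysis because the test and the SD differ from those of Section 15.2. The protocol does not support this. In ml/kg/min the adjusted model has at least the stated power whichever SD was meant, so the simplification is conservative, and the 20% allowance is applied to a requirement that errs on the safe side. A low figure, such as 78.7% at a correlation of 0.3, arises only for an unadjusted change score with 2.0 as the raw SD. No such test is planned.

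A second defence is that ml/min may be shorthand and ml/kg/min was intended. That is possible, but ml/min appears both in the endpoint section and in the summary, and nothing in the protocol says which to follow. A later analysis plan could choose a unit, but the conflict is between statements the protocol itself makes.

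A third is that body weight is fairly stable over 16 weeks, so the ml/min correlation should be high and much of the added variance is removed by adjustment. This is fair. It is the reason why the ml/min figures show uncertainty and do not establish a shortfall.

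**Conclusion.** The point holds as a conflict of units. The stated 90% power belongs to peak VO₂ in ml/kg/min, and the protocol does not show it for the ml/min endpoint it defines. It is not an arithmetic error, and the choice of t-test for sizing is not a fault.

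Under the assumptions in step 3, power in ml/min at 86 per group runs from about 82% to 99% for per-kg correlations of 0.3 to 0.7, and falls below the stated figure at correlations under about 0.47. If 2.0 is the SD of change, it stays at about 90% to 92% for correlations of 0.3 to 0.9. Mean peak VO₂, weight variation and correlation are all assumed. A reader might infer from the lower values that the trial is underpowered; the protocol contains nothing that establishes this. All of these figures also take 2.0 as correct for whichever SD it describes, and the protocol shows no data for it.

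**What to change.** - Choose one unit for the primary endpoint and use it in the Executive Summary, Section 12.1 and Section 15.5. Name it in Section 15.2 as well.
- In Section 15.5, say whether 2.0 is the SD of the raw value, of the 16-week change, or of the residual given baseline.
- If ml/kg/min is kept, the present calculation can stay, with a sentence that the t-test is a conservative approximation to the baseline-adjusted model.
- If ml/min is kept, give the difference and SD in ml/min, state the body-weight and correlation assumptions behind them, and restate the power for the Section 15.2 model.
- Keep 220 participants.

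The cost is rewording and, at most, one recalculation, with no change to enrolment or procedures. The downside is that the stated power may change and, if ml/min is kept, could fall below 90%.
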